### **5.3b Missing data**

Missing data for each questionnaire and item level missingness will be reported to help select future study outcome instruments.

## **SECTION 6 MONITORING**

### **SECTION 6.1 Data monitoring committee**

A data monitoring committee will not be formed. The intervention is of a relatively short duration and not substantially different from 'usual care' and therefore considered to be of minimal risk. Oversight of the conduct of the study will be provided by *MH*, *SH* and *DK*.

### **SECTION 6.2 Harms**

#### **6.2a Adverse events**

For this study an adverse event (AE) will be described as any unfavourable sign or symptom related to completing the study intervention.

This study involves rehabilitation after a recent LPD. No additional risks are foreseen compared to usual rehabilitation at the John Radcliffe Trauma Outpatient Physiotherapy department.

Possible (expected) complications of rehabilitation are:

Newly acquired or temporary increases in knee pain and knee swelling; delayed onset muscle soreness, persistent patellar instability and recurrent patellar dislocation. Some of these may require the need for further surgery.

Symptoms such as delayed onset muscle soreness and increases in knee pain or swelling lasting less than 1 week that do not require medical attention will not be regarded as AEs, as these are common after commencing a new exercise regime post injury. These will be managed as outlined in section 4.3a and explained in the participation information booklet. In the unlikely event of a further patellar dislocation patients will be referred to the trauma and orthopaedic service for assessment and treatment. If physiotherapist become aware of any AEs while administering the intervention, whether the AE is related to the intervention will be determined by the physiotherapist and verified by *CF* in discussion with his supervisors. All AEs will be recorded on case report forms by the participant's physiotherapist.

AEs related to the intervention will also be recorded by participant reported questionnaire at 3 month follow-up.

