- Harms. For this study harms will be defined as any unfavourable sign or symptom related to completing the study intervention. The recording of harms has been recommended in feasibility studies to inform future research design and processes. This will be measured from commencement of the intervention to 3 month follow-up as outlined in section 6.2a.
- Determine what assessment findings are consistent with a diagnosis of LPD. A member of the trauma and orthopaedic team will be required to assess the presence/absence of proposed assessment findings to include in the eligibility criteria for future studies as outlined in section 5.1. This will inform the feasibility of using these assessment findings in the eligibility criteria for future studies.

- Intervention delivery. Treatment logs will be analysed to record the duration from injury to commencing the intervention, the number of physiotherapy sessions received by participants, the duration of intervention and the exercises prescribed.

Additional demographic data will be collected as part of the study. Further information on this and the time points for data collection are outlined in section 5.1

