General health status	EQ-5D-5L	Baseline, 3 months post first physiotherapy session
Intervention delivery	Duration from LPD to first physio session, initial injury management, number of physiotherapy sessions attended, number of physiotherapy appointments participants unable to attend/did not attend, duration of the intervention from enrolment to discharge, exercises and dose of exercise	Completion of intervention

	prescribed from treatment logs completed by therapists	
Harms	Patient and staff reported adverse events including any recurrent patellar dislocation, subsequent listing for knee surgery for mechanical instability and any increases in pain or swelling resulting from the exercise intervention lasting > 1 week	From beginning of intervention to 3 months post first physiotherapy session

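### The adverse event definition already requires relatedness, so a non-serious event judged unrelated has no stated recording route, and the definition does not match the harms row in Section 5.1a

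*Combined protocol and SAP*

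**What the plan says.** Harms are a secondary objective (Section 3.2b). Section 4.4b reads "For this study harms will be defined as any unfavourable sign or symptom related to completing the study intervention", says that recording harms should inform later research, and refers to Section 6.2a for how they are measured.

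Section 6.2a gives adverse events (AEs) the same condition: "For this study an adverse event (AE) will be described as any unfavourable sign or symptom related to completing the study intervention". When a physiotherapist becomes aware of an AE, "whether the AE is related to the intervention will be determined by the physiotherapist and verified by" the lead investigator in discussion with the supervisors. It continues: "All AEs will be recorded on case report forms by the participant's physiotherapist". The second source is the participant: "AEs related to the intervention will also be recorded by participant reported questionnaire at 3 month follow-up".

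The harms row of the outcome table in Section 5.1a reads "Patient and staff reported adverse events including any recurrent patellar dislocation". It goes on to name listing for knee surgery because of instability, and "any increases in pain or swelling resulting from the exercise intervention lasting > 1 week".

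Section 6.2b defines a serious adverse event (SAE) without reference to cause and keeps an SAE judged unrelated on the case report form. Section 5.3a reports harms descriptively, and Section 4.6a sets the target at 15 participants without a power calculation.

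**The concern.** If relatedness decides whether something is an AE at all, the causal judgement comes before the record. A non-serious event that the physiotherapist attributes to the injury may then never enter the study data, and nobody reading the results could re-judge it from those data.

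That judgement is hard to make here. There is no control group, and Section 3.1a gives recurrence of 23-30% within 10 years, so the natural course of the injury is nearly always a possible explanation. The people who judge relatedness deliver or run the study, and Section 6.1 provides for no data monitoring committee.

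What is at stake is the harms count intended to inform the design of a later study. No test, threshold or progression rule depends on it.

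**Working it through.** The plan gives no expected harm rate and no harms threshold, so there is no planned figure to reproduce. The check sets the sections side by side and then adds a small calculation for scale.

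**1. Following one event through the text**

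| Event | 4.4b and 6.2a, read literally | 5.1a harms row | 6.2b |
|---|---|---|---|
| Non-serious symptom judged related | AE; on the case report form | Counted | Not applicable |
| Non-serious symptom judged unrelated | Not an AE; no recording rule | Not named | Not applicable |
| Recurrent dislocation, not serious, judged unrelated | Not an AE; no recording rule | Named, with no relatedness condition | Not applicable |
| Listing for knee surgery because of instability, not serious, judged unrelated | Not an AE; no recording rule | Named, with no relatedness condition | Not applicable |
| SAE judged unrelated | Outside the AE and harms definitions | Not addressed separately | Kept on the case report form |

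The second row is the gap. The third and fourth rows are the mismatch. The instruction to record all AEs does not close the gap, because the event has already failed the definition. The 3-month questionnaire does not close it either, because it carries the same condition.

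**2. Which section governs**

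Section 4.4b sends measurement of harms to Section 6.2a, so the relatedness condition applies to the outcome. Section 5.1a is the operational outcome table and puts no such condition on two named events. No sentence says which prevails.

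**3. Pain and swelling**

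Section 5.1a names increases lasting more than 1 week. Section 6.2a leaves out increases lasting less than 1 week only if they need no medical attention. A shorter episode that needs attention is thus an AE under 6.2a but is not named in 5.1a. The list in 5.1a is introduced as inclusive, so this is a difference of wording rather than a contradiction.

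**4. Scale**

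With n = 15 (Section 4.6a), one participant is 1/15 = 6.7 percentage points. A participant whose only event is a recurrent dislocation judged unrelated moves the harms proportion by that amount between the two sections. A participant whose unrelated event is wrongly called related moves it by the same amount upwards.

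**5. Illustration with assumed inputs**

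Let p be the true risk of a related harm and s the share of true harms wrongly judged unrelated. Neither is in the documents; p = 10-30% and s = 0-50% are assumptions. The expected number recorded is 15 × p × (1 − s). The chance of recording none is [1 − p(1 − s)]^15.

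| p | s | Expected recorded | Chance of none |
|---|---|---|---|
| 10% | 0 | 1.5 | 20.6% |
| 10% | 25% | 1.13 | 31.1% |
| 10% | 50% | 0.75 | 46.3% |
| 20% | 0 | 3.0 | 3.5% |
| 20% | 25% | 2.25 | 8.7% |
| 20% | 50% | 1.5 | 20.6% |
| 30% | 0 | 4.5 | 0.5% |
| 30% | 25% | 3.4 | 2.2% |
| 30% | 50% | 2.25 | 8.7% |

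For example, with p = 20% and s = 50%: 15 × 0.20 × 0.50 = 1.5, and 0.90^15 = 20.6%. At s = 0 nothing is lost. The table covers misjudgement in one direction only, so it shows what could happen and does not estimate bias.

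**The case against.** The best counter-argument is that Section 6.2a can be read as recording everything and then labelling it. Asking whether an AE is related presupposes that some are not, the next step is to record all AEs, and no sentence tells anyone to discard an event. This is a fair reading of intent, but it leaves the word related in the definition with no effect. The harms outcome in 4.4b would still be restricted to related events while 5.1a is not. The reading is better written down than left to each physiotherapist.

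Some safeguards do stand. The physiotherapist's judgement is verified, though not by anyone independent of the study. Participants report at 3 months without going through the physiotherapist, though only on related events. SAEs are kept whatever their cause. The study is small, descriptive and described as minimal risk, which limits the consequences.

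A reader might go further and infer any of the following, which the documents do not support:

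- **That the harms outcome is biased low.** The outcome is defined as related harms, so leaving out truly unrelated events is not bias. Bias needs misjudgement, which can go either way in an uncontrolled study, and no rate is given.
- **That Sections 5.1a and 6.2a cannot both be followed.** Recording every recurrent dislocation and surgical listing, with relatedness noted beside it, would serve both.
- **That the pain and swelling rules contradict each other.** The list in 5.1a is open.
- **That lost events are unrecoverable.** Routine physiotherapy notes are kept (Section 5.2a), and re-dislocations are referred to the trauma and orthopaedic service (Section 6.2a), so some could be traced outside the study forms.

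**Conclusion.** The point holds as a defect of definition and consistency. Sections 4.4b and 6.2a make relatedness a condition of being an AE and then ask whether the AE is related. On the literal reading, non-serious events judged unrelated have no stated route into the data, whereas unrelated SAEs do. Section 5.1a applies no such condition to recurrent dislocation or surgical listing. Harms may therefore be under-counted, or counted differently according to the section followed.

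The size and direction of any error are unknown. The only firm figure is 6.7 percentage points per participant, which assumes that the target of 15 is reached; with fewer participants each one weighs more. The conclusion also assumes that the case report form and questionnaire, which are not in the documents, follow the protocol wording. It is a cheap improvement and does not threaten the feasibility objectives.

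**What to change.** - In Sections 4.4b and 6.2a, define an AE as any unfavourable sign, symptom or event from the start of the intervention to 3 months, whatever its cause.
- Record relatedness as a separate field on the case report form, keeping the present assessment and verification steps.
- Word the 3-month questionnaire to ask about all events.
- In Section 5.3a, report all events and related events side by side, as numbers and percentages of participants.
- Reconcile Sections 4.4b, 5.1a and 6.2a so that recurrent dislocation and listing for surgery are treated alike throughout, and the wording on duration of pain and swelling agrees. Which threshold to use is for the study team.

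The cost is revised definition wording, one form field, an edited questionnaire item and a few more minor events to record for about 15 participants. The analysis stays descriptive.

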Physiotherapists will demonstrate the selected exercises followed by participants. Feedback will be provided, and participants will be asked if they would like to be recorded performing the exercises on their smartphone to increase technique compliance. The patient will be asked about their intention to adhere. If the intention is low, the barriers to adherence will be elicited and strategies to overcome them will be explored (following the principals of patient centred goal setting).

Participants will be provided with, and asked to complete, an exercise diary containing their exercises and guidance on achieving an effective dose. At the end of each session participants will be encouraged to ask questions, their understanding will be assessed and any clarifications needed will be provided. At each review session participant adherence and achievement of short-term goals will be reviewed and strategies to overcome any barriers will be explored

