#### **4.3b Intervention – concomitant care**

As the efficacy of the intervention is not in question, concomitant health care such as medication use will not be recorded, and other aspects of care will continue as usual.

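### The Harms row in 5.1a and the adverse event rule in 6.2a set different criteria for a countable pain or swelling flare, and the plan describes no data item for the medical attention that 6.2a turns on

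*Combined protocol and SAP*

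**What the plan says.** Harms are a secondary outcome. Section 4.4b defines them broadly and sends the reader elsewhere for the method: "This will be measured from commencement of the intervention to 3 month follow-up as outlined in section 6.2a". Section 6.2a gives the general definition, under which "an adverse event (AE) will be described as any unfavourable sign or symptom related to completing the study intervention", and then a carve-out: "increases in knee pain or swelling lasting less than 1 week that do not require medical attention will not be regarded as AEs".

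For flares, the Harms row of the outcome table in 5.1a names "any increases in pain or swelling resulting from the exercise intervention lasting > 1 week". That item closes a longer list, which opens in these terms: "Patient and staff reported adverse events including any recurrent patellar dislocation, subsequent listing for knee surgery for mechanical instability".

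Section 4.3b states: "As the efficacy of the intervention is not in question, concomitant health care such as medication use will not be recorded". It makes no exception for safety.

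Section 6.2a describes two routes of capture. The treating physiotherapist enters on case report forms the events that come to their notice, and the participant reports events on a questionnaire at 3 months. Section 4.3 also issues participants with "an exercise diary containing their exercises and guidance on achieving an effective dose". No use of the diary for symptoms is described.

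**The concern.** Section 6.2a lists new or increased knee pain and swelling among the expected complications of rehabilitation, so the line between a countable and a non-countable flare decides how a foreseeable harm is reported. Two sections draw that line differently. Section 5.3a says harms will be summarised descriptively but gives no counting rule that would settle the matter.

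The 6.2a rule needs two facts about each flare: how long it lasted and whether it required medical attention. The plan does not say where either is recorded. For the second, 4.3b points the other way unless it is read as not applying to adverse events. At stake is whether the harm count, which is meant to inform the design of later research, is consistent and reasonably complete.

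**Working it through.** **Step 1: the two criteria side by side.** The 6.2a carve-out applies when duration is under 1 week AND no medical attention is required. Its complement is that a flare counts if duration is 1 week or more OR medical attention is required. The 5.1a row names a flare if duration is over 1 week and is silent on medical attention. For a flare related to the intervention:

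| Duration | Medical attention required | 6.2a | Flare wording in 5.1a | Agree? |
|---|---|---|---|---|
| Under 1 week | No | Not an AE | Not named | Yes |
| Under 1 week | Yes | AE | Not named | No |
| Exactly 1 week | No | AE | Not named | No |
| Exactly 1 week | Yes | AE | Not named | No |
| Over 1 week | Either | AE | Named | Yes |

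**Step 2: does 5.1a exclude the three disagreeing cases?** Not by its terms. The row covers reported adverse events and introduces its examples with the word including, and 4.4b refers to 6.2a. Read together, the sections allow all three cases to be counted. But a stated cut-off of more than 1 week does little work if shorter flares also count, so a person completing forms from the table alone could reasonably apply it as the threshold.

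**Step 3: is there a source for the two facts?**

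- *Medical attention.* 4.3b declines to record concomitant care. Section 4.3 logs the standard acute care given in addition to the intervention, 5.1a captures listing for knee surgery, and the serious adverse event form in 6.2b would capture a hospital admission. None of these is described as recording a contact for an ordinary flare.
- *Duration.* No onset or end date is described. Staff capture depends on the physiotherapist learning of the event, and the participant's own report is made once.

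**Step 4: spacing of visits, for illustration only.** Inputs from 4.3: up to 6 sessions, with 1 or 2 more if essential, over at most 3 months. Assumptions: 3 months is 13 weeks, and sessions are evenly spaced over the whole period.

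- 6 sessions: 13/5 = 2.6 weeks, and 2.6 × 7 = 18.2 days between visits.
- 8 sessions: 13/7 = 1.86 weeks, or 13.0 days between visits.

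Fewer sessions over the same period would widen the gap. A flare lasting 1 to 2 weeks could therefore begin and settle between visits. It could still be mentioned at the next one, so this shows reliance on short recall plus a prompt that is not described. It does not show loss of the event, and it has no bearing on the mismatch in Step 1, because flares over 1 week count under both sections.

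**Step 5: size.** The documents give no flare rate, so the expected number of affected events cannot be computed. If harms are reported as a percentage of the target 15 participants, one participant changing category moves the result by 1/15 = 6.7 percentage points.

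**The case against.** A reader might infer that short flares needing medical attention are misclassified as no harm. The documents do not support that: 6.2a makes them adverse events, 4.4b refers to 6.2a, and the 5.1a list is open. The misclassification follows only if the list is treated as exhaustive.

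A reader might also infer that 4.3b forbids recording what 6.2a needs. It does not say so. It is a general statement, its reason is efficacy, its example is medication, and it does not mention adverse events. Section 6.2a specifically requires adverse events to go on case report forms, and other sections record some health-care contact.

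Nor is capture left wholly to recall at 3 months. Physiotherapists record events during treatment, adherence and barriers are reviewed at each review session, and 4.3a sets out how increased symptoms are handled, with review at the next session. The forms themselves are not in the documents and may already ask about duration and care. Finally, harms are a secondary, descriptive outcome in a small study.

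All of this stands, and it limits the point to inconsistent counting and possible under-capture. It does not remove the difference in wording, supply a described data item, or give 4.3b a safety exception.

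**Conclusion.** The point holds as a modest one. The flare criteria in 5.1a and 6.2a differ in three of the five cases in the table and need to be reconciled. The 6.2a rule rests on duration and medical attention, and the plan describes no item for either, while 4.3b could be read as discouraging the collection of one of them. The consequence is a risk that the same events are counted differently, or that some are not captured. A definite downward bias in the harm count is not shown, and its size cannot be stated without a flare rate. The 6.7-point step assumes that all 15 participants are recruited and that harms are expressed per participant; with fewer participants the step is larger. The part of the conclusion about missing data items depends on forms that could not be seen.

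**What to change.** 1. Reconcile the two sections so that the Harms row of 5.1a uses the 6.2a recording criterion in 6.2a's own terms. A flare is left out only if it lasts less than 1 week and does not require medical attention; this also settles a flare of exactly 1 week. Keep the word require: replacing it with sought would change the definition, not align it.
2. State in 4.3b that the decision not to record concomitant care does not limit the recording of health-care contact for a possible adverse event.
3. Add three fields to the exercise diary already issued: the date a pain or swelling increase began, the date it settled, and whether medical attention was needed. Have the physiotherapist transfer these to the case report form at each visit. If the case report form and 3-month questionnaire already hold equivalent items, say so in 6.2a.

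These changes concern recording only and alter no clinical management. The cost is two wording changes and three diary fields, slight extra burden for participants, and possibly a higher reported harm count. The protocol gives recruitment as pending (1.2) and ethical approval as still to be sought (7.1), so on its own account the change can be made before the first participant enrols.

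### In-session adverse-event capture is passive and the only direct enquiry described is one 3-month questionnaire; a standard question at each session would give more complete and interpretable harms data

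*Combined protocol and SAP*

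**What the plan says.** Section 6.2a describes two routes for adverse events.

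- **During treatment.** The sentence on in-session events opens "If physiotherapist become aware of any AEs while administering the intervention" and goes on to say who judges relatedness (the physiotherapist, with verification). The next sentence is the recording rule: "All AEs will be recorded on case report forms by the participant's physiotherapist".
- **At 3 months.** "AEs related to the intervention will also be recorded by participant reported questionnaire at 3 month follow-up".

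The Harms row of the table in 5.1a draws on both routes: "Patient and staff reported adverse events including any recurrent patellar dislocation, subsequent listing for knee surgery for mechanical instability", together with exercise-related increases in pain or swelling that last more than 1 week. Section 4.4b sets the window: "This will be measured from commencement of the intervention to 3 month follow-up as outlined in section 6.2a".

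Section 4.3 gives the content of a review session: "At each review session participant adherence and achievement of short-term goals will be reviewed and strategies to overcome any barriers will be explored". Section 4.3a covers what happens once pain or swelling has increased. Neither section schedules a question about harms. Section 5.1c provides at least one reminder for unreturned postal questionnaires and follow-up contact for incomplete data. Section 5.3b reports missingness by questionnaire and by item.

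**The concern.** Read literally, the plan has the physiotherapist act on events that come to notice, without asking about them. What comes to notice will vary with how much each physiotherapist enquires. The questionnaire partly compensates, but it has two limits. The participant must remember, up to about 3 months later, whether an increase in pain or swelling lasted more than 1 week. The participant must also decide whether the event was related to the intervention, a judgement that 6.2a gives to the physiotherapist, with verification, for events noticed in a session.

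Section 4.4b says harms are recorded to inform the design of later research. Section 3.1b notes that earlier reported programmes did not use, or did not clearly describe, hopping, change of direction or sport-specific exercise, so there is little earlier harms experience to draw on. A low count from this study would be read as reassurance, and the reader needs to know how far it reflects asking.

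**Working it through.** The plan states no figure on this point, so there is none to reproduce. The check is first of the text, then of what can and cannot be quantified.

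**1. Where participants are asked about harms**

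| Place | Content | Harms question described? |
|---|---|---|
| 4.3, review sessions | Adherence, short-term goals, barriers | No |
| 4.3a | Response once pain or swelling has increased | No; reactive |
| 4.4b and 5.1a, treatment logs | Timing, session counts, duration, exercises, dose | No |
| 6.2a, sessions | Action if the physiotherapist becomes aware | No; conditional |
| 6.2a, 3 months | Participant questionnaire | Yes, once, for related events |

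The case report forms and clinician handbook are not in the documents, so a prompt there cannot be excluded.

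**2. Recall interval.** Take 3 months as about 13 weeks and assume six sessions (4.3), evenly spaced. The questionnaire alone asks for recall of up to 13 weeks. A question at each session after the first covers 13 / 5 = 2.6 weeks.

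**3. Why the number asked matters.** For zero events among n people asked, the exact two-sided 95% upper limit is 1 − 0.025^(1/n).
- n = 15: 21.8%.
- n = 7: 41.0%. This uses, for illustration only, the 52% attrition that 3.1b reports for an earlier exercise trial: 15 × 0.48 = 7.2.

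The same count of zero supports quite different statements depending on how many were asked.

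**4. Whether the shortfall can be sized.** Let d be in-session detection, r questionnaire return and s recall. If the two routes are independent, combined capture is 1 − (1 − d)(1 − r × s). The documents give no value for d, r or s and do not establish independence, so everything here is assumed.

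| d | r = 1, s from 0.5 to 1 | r = 0.48, s from 0.5 to 1 |
|---|---|---|
| 0.25 | 63–100% | 43–61% |
| 0.50 | 75–100% | 62–74% |
| 0.75 | 88–100% | 81–87% |

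For participants who complete follow-up, r = 1. With d = 0.5 and s = 0.6, capture is 1 − 0.5 × 0.4 = 0.80. If 5 of 15 truly had a qualifying event, 5 × 0.80 = 4.0 of 15 (26.7%) would be reported instead of 33.3%. With d = 0.3 the figure is 5 × 0.72 / 15 = 24.0%; with d = 0.7 it is 5 × 0.88 / 15 = 29.3%. The exact 95% intervals for 4/15 (7.8–55.1%) and 5/15 (11.8–61.6%) overlap heavily. Capture runs from 43% to 100% across the table, so the assumptions decide the answer.

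**5. Workload.** Six sessions: 5 × 15 = 75 enquiries. Eight sessions, the most that 4.3 allows: 7 × 15 = 105.

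**The case against.** The case for leaving the plan alone has real force. The conditional sentence in 6.2a mainly settles who judges relatedness; recording is covered by the next sentence, which applies to all adverse events. Sessions involve a physical assessment, treatment aimed at swelling, and discussion of barriers, so many problems will surface anyway. A further dislocation or listing for surgery is hard to forget and is likely to reach the team by other routes. The outcome is descriptive, in 15 people, in a programme that 6.1 regards as minimal risk, and no stated decision turns on it.

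Much of this stands. It confines the recall problem mainly to pain or swelling lasting over 1 week, and it rules out several stronger readings:

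- *That absence of harm cannot be told from not asking anywhere in the study.* Questionnaire returners have a self-reported record, non-return is chased (5.1c) and missingness is reported (5.3b). The ambiguity belongs to session records, and to non-returners, who have only the passive route.
- *That no session will include a harms question.* The forms and handbook are not in the documents; one can say only that the protocol describes none.
- *That serious-event reporting waits on chance awareness.* Section 6.2b requires a form within 24 hours and carries no such condition.
- *That harms are under-counted by a known amount.* No input for that calculation is in the documents.

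The objection does not supply a scheduled enquiry, and it does not remove the questionnaire's dependence on long recall and on self-judged relatedness.

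**Conclusion.** The point holds in limited form. As written, in-session capture is passive and the only direct enquiry described is a single questionnaire at 3 months. Harms are likely to be captured less completely than the existing visits would allow, chiefly pain or swelling lasting over 1 week, and a blank session record is ambiguous. This rests on the text of 4.3, 4.3a, 4.4b, 5.1a and 6.2a, and on the general expectation that asking finds more than waiting to be told.

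The size of any shortfall cannot be derived from the documents; the figures above are illustrations. Each missed case moves the reported percentage by 1/15 = 6.7 points, well inside the statistical uncertainty at this sample size. The plan should be changed because the remedy is cheap and harms are a stated objective. The gap does not undermine the study.

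**What to change.** **Section 6.2a.** Replace the conditional opening with a scheduled enquiry. At every session after the first, the physiotherapist asks a standard yes/no question about events since the last session: recurrent dislocation, listing for knee surgery, an increase in pain or swelling that meets the protocol's existing adverse-event threshold, and any other event. The answer, including a no, and the date go on the adverse-event case report form that 6.2a already uses, so that no second log needs reconciling. The existing process for judging and verifying relatedness stays. If the form already carries such a prompt, one sentence in 6.2a saying so is enough.

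**Section 5.3a.** Report harms by source (session enquiry, 3-month questionnaire), each with the number of participants asked as the denominator. Count once any event reported by both routes.

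Keep the questionnaire, since it alone covers the time between a participant's last session and 3 months. Adverse-event thresholds and clinical care are unchanged.

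**Cost.** Protocol wording and a few tick boxes; about a minute per enquiry (assumed), at most 75 enquiries or 105 with eight sessions each; no extra visits or staff. The reported event count will probably be higher than under passive capture, and the report should say that events were actively sought.
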